9.4.2 Medically Attended Adverse Events

For subjects that received ARCT-021 in the parent study, the collection of MAAE will begin at the Screening visit, when MAAE (and SAE) occurring since completion of the Parent Study will be solicited to ensure continuity of safety follow-up from the Parent Study to this study, and stop at the end of the subject's follow-up period which is defined as the subject's last protocol-specified study visit.

For subjects who receive ARCT-021 in this study and who did not receive ARCT-021 in the Parent Study, the collection of MAAEs will begin after the subject has received ARCT-021 and stop at the end of the subject's follow-up period. MAAEs that occur prior to administration of ARCT-021, including those that occurred between leaving the Parent Study and dosing in this Study will be recorded as medical history.

MAAEs that also fulfil the criteria of an SAE should be reported to the Sponsor or designee within 24 hours of the Study Center's first knowledge of the event (Section 9.4.1).

9.4.3 Non-Serious Adverse Events

For subjects who receive ARCT-021 in this study and who did not receive ARCT-021 in the Parent Study, the recording of non-serious AEs will begin after the subject has received ARCT-021 and will stop 28 days after the last dose of ARCT-021, with the exception of ongoing adverse events that worsen in severity and/or become serious, which will continue to be recorded. AEs that occur prior to administration of ARCT-021, including those that occurred between leaving the Parent Study and dosing in this Study will be recorded as medical history.

For subjects who receive ARCT-021 in this study and who also received ARCT-021 in the Parent Study, the recording of non-serious AEs will begin from the time the subject received ARCT-021 in the Parent Study and will stop 28 days after the dose of ARCT-021 in this study, with the exception of ongoing adverse events that worsen in severity and/or become serious, which will continue to be recorded. Any AEs that occurred between leaving the Parent Study and entering this study will be recorded as AEs.

For subjects who do not receive ARCT-021 in this study, only medically attended non-serious events will be recorded as described above (Section 9.4.2). The Investigator will monitor each subject closely and record all observed or volunteered AEs in the EDC.

9.4.4 Evaluation of Adverse Events (Serious and Non-Serious)

The Investigator's opinion of the following must be documented on the Adverse Event Case Report Form:

9.4.4.1 Relationship to the Study Drug

Reactogenic events with onset within 7 days of injection of ARCT-021 will be regarded as related.

For other events, the event's relationship to the Study Drug is characterised by one of the following:

- **Related:** There is clear evidence that the event is related to the use of Study Drug, e.g., confirmation by positive re-challenge test
- **Possibly Related:** The event cannot be explained by the subject's medical condition, concomitant therapy, or other causes, and there is a plausible temporal relationship between the event and Study Drug administration
- **Unlikely Related:** An event for which an alternative explanation is more likely (e.g., concomitant medications or ongoing medical conditions) or the temporal relationship to Study Drug administration and/or exposure suggests that a causal relationship is unlikely (For reporting purposes, Unlikely/Remote will be grouped together with Not Related)
- **Not Related:** The event can be readily explained by the subject's underlying medical condition, concomitant therapy, or other causes, and therefore, the Investigator believes no relationship exists between the event and Study Drug

9.4.4.2 Severity

The severity of AEs and SAEs will be graded by the Investigator according to the Toxicity Grading Scale for Healthy Adult and Adolescent Volunteers Enrolled in Preventive Vaccine Clinical Trials, Sept 2007, where applicable.

Any AE not listed in this scale will be graded as follows:

- **Mild:** The event is easily tolerated by the subject and does not affect the subject's usual daily activities
- **Moderate:** The event causes the subject more discomfort and interrupts the subject's usual daily activities
- **Severe:** The event is incapacitating and causes considerable interference with the subject's usual daily activities

If the event is an SAE, then all applicable seriousness criteria must be indicated (criteria listed in Section 9.3.3).

9.4.4.3 Action Taken with Study Drug

Action taken with Study Drug due to the event is characterised by one of the following.

- **Not Applicable:** This applies to all AE occurring in subjects that do not receive ARCT-021 in this study. For subjects who receive ARCT-021 in this study, this applies if a SAE/AE was reported during screening period prior to ARCT-021 administration or in the Post-Treatment Period following the Administration period
- **Dose Not Changed:** No changes were made to dose of ARCT-021
- **Drug Withdrawn:** ARCT-021 was discontinued and not restarted
- **Drug Interrupted:** Dosing frequency was temporarily interrupted/changed or delayed due to the AE and restarted at the same dose level

9.4.4.4 Treatment Given for Adverse Event

Any treatment (e.g., medications or procedures) given for the AE should be recorded on the Adverse Event eCRF. Treatment should also be recorded on the concomitant treatment or ancillary procedures eCRF, as appropriate.

9.4.4.5 Outcome of the Adverse Event

The AE's outcome is characterised by one of the following:

- **Fatal:** Subject died (the date of death should be entered as the SAE resolution date)
- **Not Recovered/Not Resolved:** Subject terminates from the trial and the AE continues
- **Recovered/Resolved:** Subject recovered completely from the AE
- **Recovered/Resolved with Sequelae:** The signs/symptoms of the reported AE have improved but not completely resolved, and a new baseline for the subject is established since full recovery is not expected.
- **Recovering/Resolving:** The signs/symptoms of the reported AE have improved but not completely resolved, but full recovery is expected.
- **Unknown:** The outcome of the reported is not available, e.g., subject is lost to follow-up.

9.4.4.6 Follow-up of Adverse Events

During the study period, the Investigator should follow each AE until the event has resolved to baseline grade or better, the event is assessed as stable, the subject is lost to follow-up, or the subject withdraws consent. Every effort should be made to follow all SAEs until a final outcome can be reported (Section 9.4.1). SAEs that remain ongoing past the subject's last protocol-specified follow-up visit will be evaluated by the Investigator and Sponsor. If the Investigator and Sponsor agree the subject's condition is unlikely to resolve, the Investigator and Sponsor will determine the follow-up requirement.

Resolution of AE (with dates) should be documented on the Adverse Event eCRF and in the subject's medical record to facilitate source data verification.

Sponsor Follow-Up

For SAEs and CESIs that have occurred in subjects who have been vaccinated with ARCT-021 within the last 12 months, the Sponsor or a designee should follow-up by telephone, fax, email, and/or a monitoring visit to obtain additional case details and outcome information (e.g., from hospital discharge summaries, consultant reports, autopsy reports) in order to perform an independent medical assessment of the reported case.

9.5 Procedures for Handling Special Situations

9.5.1 Abnormalities of Laboratory Tests

Clinically significant abnormal laboratory test results may, in the opinion of the Investigator, constitute or be associated with an AE. Examples of these include abnormal laboratory results that are associated with symptoms, or require treatment, e.g., bleeding due to thrombocytopenia, tetany due to hypocalcemia, or cardiac arrhythmias due to hyperkalemia. Whenever possible, the underlying diagnosis should be listed in preference to abnormal laboratory values as AEs. Clinically significant abnormalities will be monitored by the Investigator until the parameter

returns to its baseline value or until agreement is reached between the Investigator and Sponsor Medical Monitor (or designee) that further follow-up is not required. Laboratory abnormalities deemed not clinically significant (NCS) by the Investigator should not be reported as AEs. Similarly, laboratory abnormalities reported as AEs by the Investigator should not be deemed NCS on the laboratory sheet.

The Investigator is responsible for reviewing and signing all laboratory reports. The signed clinical laboratory reports will serve as source documents and should include the Investigator's assessment of clinical significance of out of range/abnormal laboratory values.

9.5.2 Prescheduled or Elective Procedures or Routinely Scheduled Treatments

A prescheduled or elective procedure or a routinely scheduled treatment will not be considered an SAE, even if the subject is hospitalized; the Study Center must document all of the following:

- The prescheduled or elective procedure or routinely scheduled treatment was scheduled (or was on a waiting list to be scheduled) prior to obtaining the subject's consent to participate in the study
- The condition that required the prescheduled or elective procedure or routinely scheduled treatment was present before and did not worsen or progress in the opinion of the Investigator between the subject's consent to participate in the study and the timing of the procedure or treatment
- The prescheduled or elective procedure or routinely scheduled treatment is the sole reason for the intervention or hospital admission

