9.4 Monitoring and Recording Adverse Events

Any pre-existing conditions or signs and/or symptoms present in a subject prior to the first injection of ARCT-021 should be recorded as Medical History and not recorded as AEs unless the pre-existing condition worsened. The Investigator should always group signs and symptoms into a single term that constitutes a **single unifying diagnosis** if possible. Before a diagnosis is confirmed, all symptoms should be reported as separate AEs.

Any AE that includes a new diagnosis of a chronic medical condition that was not present or suspected prior to enrollment, will be categorized as a new onset of chronic disease (NOCD).

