9.4.1 Serious Adverse Events

In the interest of subject safety, and in order to fulfill regulatory requirements, all SAEs (regardless of their relationship to Study Drug) should be reported to the Sponsor or designee within 24 hours of the Study Center's first knowledge of the event.

For subjects that received ARCT-021 in the parent study, the collection of SAE will begin at the Screening visit, when SAE (and MAAE) occurring since completion of the Parent Study will be solicited to ensure continuity of safety follow-up from the Parent Study to this study, and stop at the end of the subject's follow-up period which is defined as the subject's last protocol-specified study visit.

For subjects who receive ARCT-021 in this study and who did not receive ARCT-021 in the Parent Study, the collection of SAEs will begin after the subject has received ARCT-021 and stop at the end of the subject's follow-up period. SAEs that occur prior to administration of ARCT-021, including those that occurred between leaving the Parent Study and dosing in this Study, will be recorded as medical history.

SAEs considered to be related or possibly related to Study Drug and any deaths will continue to be reported for 30 days after the subjects last study visit. SAEs will be reported within the electronic data capture system (EDC) whenever possible. If the EDC is not available, the SAE can be initially reported using a paper Initial Serious Adverse Event Form, which should be faxed or emailed to the Sponsor or designee. The SAE reporting instructions, including the fax number and email address for submitting paper forms can be found in the Investigator site file for the study. If the Investigator is reporting by telephone, it is important to speak to someone in person versus leaving a message.

Detailed information should be actively sought and included on Follow-Up Serious Adverse Event Forms as soon as additional information becomes available. All SAEs will be followed until resolution. SAEs that remain ongoing past the subject's last protocol-specified follow-up visit will be evaluated by the Investigator and Sponsor. If the Investigator and Sponsor agree the subject's condition is unlikely to resolve, the Investigator and Sponsor will determine the follow-up requirement.

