10.5.3 Safety Analysis

The primary objective of the study is the evaluation of the safety and tolerability of ARCT-021. The primary endpoints that align with this objective are:

- Solicited AEs for 7 days after vaccination (Cohort 1), summarized by toxicity grade
- Unsolicited AEs for 28 days after vaccination (Cohort 1), summarized by mild/moderate/severe and relationship to ARCT-021
- SAEs through Day 197 (Cohort 2; 12 months after ARCT-021 vaccination in ARCT-021-01 study), summarized by relationship to ARCT-021
- SAEs through Day 365 (Cohort 1; 12 months after ARCT-021 vaccination in ARCT-021-02 study), summarized by relationship to ARCT-021
- MAAEs through Day 197 (Cohort 2; 12 months after ARCT-021 vaccination in ARCT-021-01 study), summarized by relationship to ARCT-021
- MAAEs through Day 365 (Cohort 1; 12 months after ARCT-021 vaccination in ARCT-021-02 study), summarized by relationship to ARCT-021
- NOCDs through Day 197 (Cohort 2; 12 months after ARCT-021 vaccination in ARCT-021-01 study), summarized by relationship to ARCT-021
- NOCDs through Day 365 (Cohort 1; 12 months after ARCT-021 vaccination in ARCT-021-02 study), summarized by relationship to ARCT-021
- Safety laboratory assessments through 28 days after vaccination (Cohort 1), summarized by toxicity grade (where relevant)

- Vital signs assessments through day 365 (Cohort 1; 12 months after ARCT-021 vaccination in ARCT-021-02 study) summarized by toxicity grade

To support the continued characterization of ARCT-021 tolerability and safety when administered as a single dose, the following summaries will be provided:

- Summary of solicited (7 days after vaccination) and unsolicited AEs 28 days after vaccination)
- Summary of MAAEs, NOCDs, SAEs through 12 months after vaccination

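### For subjects vaccinated in the Parent Study, the elective-procedure exemption in Protocol 9.5.2 is timed from extension consent, after exposure, so some planned admissions for post-vaccination conditions can leave the SAE count

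*Protocol*

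**What the plan says.** Protocol 9.5.2 sets three conditions, all of which the site must document, for a planned procedure not to count as an SAE even with hospitalisation:

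1. The procedure "was scheduled (or was on a waiting list to be scheduled) prior to obtaining the subject's consent to participate in the study".
2. The underlying condition "was present before and did not worsen or progress in the opinion of the Investigator between the subject's consent to participate in the study", the interval ending when the procedure takes place.
3. The procedure "is the sole reason for the intervention or hospital admission".

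Three other parts of the Protocol use a different reference point:

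- Section 9.4: conditions "present in a subject prior to the first injection of ARCT-021 should be recorded as Medical History and not recorded as AEs", unless they worsen.
- Section 9.4.1, for Parent Study vaccinees: "the collection of SAE will begin at the Screening visit, when SAE (and MAAE) occurring since completion of the Parent Study will be solicited".
- Section 10.5.3, a primary endpoint: "SAEs through Day 197 (Cohort 2; 12 months after ARCT-021 vaccination in ARCT-021-01 study), summarized by relationship to ARCT-021".

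SAP 8.1.1 counts events in Cohorts 1b and 2 as treatment-emergent from exit of the Parent Study. SAP 8.1.4 repeats the hospitalisation criterion for an SAE and does not mention the exemption. Neither document sets a different reference date in 9.5.2 for subjects already exposed.

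**The concern.** An exemption timed from consent works when consent comes before exposure, because anything booked by then cannot be due to the vaccine. In this extension that holds only for subjects whose first ARCT-021 dose is given here (Cohort 1a). Cohort 2 was vaccinated months before consenting. For these subjects the rule can treat a condition that arose after vaccination as if it had been there beforehand.

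The SAE count to 12 months after Parent Study vaccination is a primary endpoint for Cohort 2. The exemption can only take events out of that count. It is applied at the site, so an exempted admission may never reach the SAE tables, and the analysis could not put it back. The 24-hour reporting in 9.4.1 and the sponsor's independent causality assessment in 9.2 are also tied to SAE status.

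**Working it through.** **Which study is meant.** The Protocol calls ARCT-021-01 the Parent Study throughout, and its glossary starts on-study status at signing of consent. Consent in 9.5.2 is therefore most naturally consent to ARCT-021-02, although the section does not say so.

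**Where consent falls relative to vaccination.** Inputs are SAP 5.3.2 (Parent Study of 57 days for Cohorts A to D2 and 85 days for E to H, then a nominal 90-day gap) and Protocol 3.8.1 and Appendix 1 (screening within 28 days before Day 1, so consent is placed 1 to 28 days before it). The second dose in E to H is taken as Parent Study Day 29. That is inferred from Protocol Table 5, where Day 43 is the 15-day timepoint; SAP Table 1 shows Day 15 for these cohorts, so it is an assumption.

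The SAP's own figures reproduce: 57 + 90 = 147 and 85 + 90 = 175.

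| | A to D2 | E to H |
|---|---|---|
| Extension Day 1, as Parent Study day | 147 | 175 |
| Consent, as Parent Study day | 119 to 146 | 147 to 174 |
| Last dose, as Parent Study day | 1 | 29 |
| Days from last dose to consent | 118 to 145 | 118 to 145 |
| Days from first dose to consent | 118 to 145 | 146 to 173 |
| Extension Day 197, as Parent Study day | 147 + 196 = 343 | 175 + 196 = 371 |
| Days from last dose to Day 197 | 342 | 342 |

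Consent therefore falls 118/342 = 34.5% to 145/342 = 42.4% of the way from last dose to Day 197. The stretch from Parent Study end to consent is 90 − 28 = 62 to 90 − 1 = 89 days. The SAP is a day apart on its own labels (extension Day 29 is 175/203 in Table 3 and 176/204 in 7.2), which makes no difference here.

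**Applying the rule to four cases.**

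- *Cohort 2, surgery after consent.* The condition starts after vaccination, surgery is booked before consent and done later, with no worsening and no other reason for admission. All three conditions are met, so it is not an SAE. Timed from first injection, the exemption would fail and the admission would count.
- *Cohort 2, admission completed between the studies.* Condition 1 is met. Condition 2 asks about worsening between consent and procedure, an interval that does not exist. Section 9.4.1 solicits SAEs from this period, but 9.5.2 does not say whether this one counts.
- *Cohort 1b.* Exclusion 4 bars new clinically significant abnormalities, including major surgery, since enrolment in the Parent Study, and inclusion 4 requires good health. Most subjects of this kind would not be dosed here.
- *Cohort 1a.* Consent precedes first exposure, so the rule does its job.

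**What one event would do.** The documents give neither an SAE rate nor the size of Cohort 2, so the n below are assumed. The figure 106 is the SAP's full enrolment and includes other cohorts. The exact 95% upper limit is the 0.975 quantile of Beta(x + 1, n − x).

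| n | Upper limit, 0 events | Upper limit, 1 event |
|---|---|---|
| 30 | 11.6% | 17.2% |
| 50 | 7.1% | 10.6% |
| 70 | 5.1% | 7.7% |
| 106 | 3.4% | 5.1% |

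**The case against.** The strongest reply is that little is lost. Section 9.5.2 removes SAE status from the procedure only; it does not turn the disease into medical history. The disease can still be an MAAE or NOCD. Both are solicited back to Parent Study completion, both are primary safety categories in 10.5.3, and both receive narratives under SAP 8.1.5 and 8.1.6. It can also be serious on another criterion in 9.3.3, in the view of either the investigator or the sponsor. Sections 9.4 and 9.5.2 decide different questions, so a site can follow both. Events during the Parent Study fell under that study's own safety collection, which is not visible here.

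Most of this stands. The two sections are out of line rather than impossible to apply together, and the signal need not disappear. But the alternative routes are not certain: SAP 8.1.5 defines an MAAE by an unscheduled visit, which a planned admission may not be. SAEs are also their own primary endpoint line, and capture in another category does not correct that count.

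A reader might also infer that every planned admission for a post-vaccination condition is removed, or that the whole 90-day gap is exempt. The text supports neither. Procedures booked after consent, conditions that worsened after it and admissions with another reason remain SAEs; for admissions completed before consent the rule is unclear.

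**Conclusion.** The point holds in a limited form. As written, 9.5.2 can exempt an admission for a condition that began after ARCT-021 vaccination, provided it was booked before extension consent, the condition did not worsen after that consent, and nothing else caused the admission. This matters chiefly for Cohort 2 and much less for Cohort 1b. It does not fit the exposure-based logic of 9.4, 9.4.1 and 10.5.3, and it leaves admissions between the studies unresolved.

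The size cannot be computed and is probably a few events at most. A reader might take 34.5% to 42.4% as the share of SAEs at risk. It is a share of nominal calendar time, part of it spent inside the Parent Study, and says nothing about how many planned admissions occurred. Nor do the documents support equal bias in Cohorts 1b and 2. Besides the eligibility filter, the Protocol's 12-month SAE endpoint for Cohort 1 runs from the dose given in this study, and the SAP presents Cohort 1b events before that dose separately.

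The conclusion rests on reading consent in 9.5.2 as consent to ARCT-021-02, and the day counts rest on the SAP's nominal intervals. The case for acting is that any error goes one way, falls on a primary safety endpoint and is cheap to remove.

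**What to change.** In Protocol 9.5.2, for subjects who received ARCT-021 in the Parent Study, time both the scheduling condition and the no-worsening condition from the first injection of ARCT-021, as 9.4 already does. Keep the consent reference for Parent Study placebo recipients. This also gives condition 2 a real interval for admissions that took place between the studies.

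Before the final database lock, re-check any admission already exempted under 9.5.2 in subjects vaccinated in the Parent Study.

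The cost is a one-sentence clarification of a reporting definition and a review of the exempted admissions, whose number the documents do not give. The SAE count may become slightly less favourable.

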9.5.3 Dosing Errors

Study Drug errors (including overdose, underdose, and administration error) should be documented as Protocol Deviations. A brief description should be provided in the deviation, including whether the subject was symptomatic (list symptoms) or asymptomatic, and the event accidental or intentional.

Dosing details should be captured on the Dosing Case Report Form. If the subject receives a dose of Study Drug that exceeds protocol specifications and the subject is symptomatic, then the symptom(s) should be documented as an AE and be reported per Section 9.4.

An overdose is the accidental or intentional use of a drug in an amount higher than the dose being studied. An overdose or incorrect administration of study treatment is not itself an adverse event, but it may result in an adverse event. All adverse events associated with an overdose or incorrect administration of Study Drug should be recorded on the Adverse Event eCRF. If the associated adverse event fulfills seriousness criteria, the event should be reported to the Sponsor immediately (i.e., no more than 24 hours after learning of the event).

Should an overdose occur, the Investigator or designee should refer to the Guidance to Investigator's section of the Investigator's Brochure and contact the Sponsor or designee within 24 hours.

